#### 7.5.6. Unscheduled Visits

If necessary to evaluate adverse events or HAV complications, additional visits may be scheduled at the discretion of the investigator. At a minimum, HAV status on clinical examination and Doppler ultrasound and adverse events will be recorded.

If, at any of the scheduled visits, duplex ultrasound surveillance suggests the development of  $a \ge 50\%$  stenosis within the HAV but immediate intervention is not required, closer follow up should be considered. Intervention to manage any such stenosis is at the discretion of the investigator taking into account the degree and rate of progression of the stenosis.

# 7.6. Medical Care during the Study and upon Study Termination

Optimal medical therapy should be continued during the study. This should include:

- An exercise program
- Smoking cessation advice and therapy
- Management of diabetes, hypertension and dyslipidemias according to current guidelines.
- Antiplatelet therapy (see Section 6.8.1)

After the final study visit at Month 60, patients will not receive any further study-specific treatment. They will be treated by their physician in a way that is appropriate for them.

# 7.7. Histological Examination of Resected HAV Material

If all or part of the HAV is resected, it should, wherever possible, be retained for future histological examination. Instructions for preservation, storage and shipping of this material will be provided separately in a procedures manual. If a patient dies with an HAV in situ and it is feasible to obtain a fresh postmortem sample of the HAV, this should be attempted in accordance with local regulations.

# 8. SAFETY ASSESSMENTS AND ADVERSE EVENTS

Safety of the HAV will be assessed in terms of:

- Aneurysm formation
- Pseudoaneurysm formation
- Anastomotic bleeding or spontaneous rupture
- HAV infection
- Need for HAV removal
- Significant inflammation at the implantation site
- Other adverse events
- Laboratory parameters (clinical chemistry, hematology, and coagulation)
- Increase from baseline in PRA

### 8.1. Adverse Event Definition

An AE is any untoward medical occurrence in a patient administered an IMP and which does not necessarily have a causal relationship with the IMP. An AE can, therefore, be any unfavorable and unintended sign (e.g. an abnormal laboratory finding), symptom, or disease temporally associated with the use of an IMP, whether or not related to the IMP. Any worsening of the patient's disease under study or other medical conditions will also be considered to be an AE, unless it is within the normal range of disease fluctuation for that patient.

# 8.2. Serious Adverse Event Definition

An AE is considered "serious" if, in the view of either the investigator or Sponsor, it:

- Results in death
- Is life-threatening
  - The term "life-threatening" in the definition of "serious" refers to an event in which the patient was at immediate risk of death at the time of the event; it does not include an adverse event that had it occurred in a more severe form, might have caused death.

- Requires patient hospitalization or prolongation of existing hospitalization
  - This is defined as the patient being hospitalized for 24 hours or more or the patient's hospital stay being prolonged for at least an additional overnight stay.
- Requires intervention to prevent permanent damage
- Results in persistent or significant disability/incapacity
- Is a congenital anomaly/birth defect
- Important Medical Events
  - For the purpose of this study, this includes any event involving the HAV that results in a surgical or endovascular radiological intervention. The event(s) which caused the procedure should be reported as an SAE. For example: in the event of HAV thrombosis, the thrombosis would be considered the SAE; any associated stenoses (or other associated findings) that are present would be considered AEs.

Medical and scientific judgment should be exercised in deciding whether expedited reporting to the sponsor is appropriate in other situations, such as important medical events that may not be immediately life-threatening or result in death or hospitalization but may jeopardize the patient or may require medical or surgical intervention to prevent one of the other outcomes listed in the definition above. These may also be considered to be SAEs.

Note: Hospitalization for the surgery to implant the HAV is not a SAE. However, prolongation of the initial hospitalization due to an AE will be considered a SAE.

### 8.3. Suspected Unexpected Serious Adverse Reaction

A suspected unexpected serious adverse reaction (SUSAR) is any adverse drug reaction that is serious (as defined in Section 8.2), unexpected (is not listed in the IB or is not listed at the specificity or severity that has been observed) and suspected (meaning there is a reasonable possibility that the IMP caused the adverse event).

#### 8.4. Events of Special Interest

Events of Special Interest are:

- HAV occlusion (thrombosis)
- HAV spontaneous rupture

- latrogenic injuries are not an Event of Special Interest and should be reported as an AE
- HAV infection
- HAV abandonment
- HAV aneurysm
- HAV pseudoaneurysm
- HAV excision (partial or complete)

# 8.5. Reporting of Adverse Events

At each evaluation, the investigator will determine whether any AEs have occurred. The patient will be questioned in a general way and no specific symptoms will be suggested. If any AEs have occurred, they should be documented in the patient's medical chart and recorded on the AE pages of the eCRF. If known, the diagnosis should be recorded in preference to the listing of individual signs and symptoms. All serious adverse events (SAEs should be reported to the Safety Contract Research Organization (CRO) within 24 hours from the time the investigator or study personnel first become aware of the event.

AE reporting begins from implantation of the HAV (the moment the patient undergoes anesthesia) and ends at the conclusion of the Month 12 or ET visit unless an unresolved AE is still being followed.

During the long term follow up period from post Month 12 through Month 60, only the following will be reported by the investigator:

- All SAEs
- All Events of Special Interest (Section 8.4)

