## 4.2. Study Endpoints

Endpoints will be evaluated at multiple time points up to 60 months after HAV implantation. The primary analysis of the study will be conducted on the earlier of a) when the final subject enrolled reaches 12 months post-implant or b) all subjects enrolled in the initial 36 month accrual period have reached 12 months post-implant.

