#### 4.2.1. **Primary Endpoints**

#### Safety:

- Incidence of HAV aneurysm formation (true or pseudo)
- Anastomotic bleeding or spontaneous rupture
- HAV infection
- HAV removal
- Significant local inflammation at the HAV implantation site
- Frequency and severity of adverse events

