3.4 Interim Analysis

Data Monitoring Committee (DMC) reports will be provided during the course of the study.

Statistical Analysis Plan	Final Analysis
CLN-PRO-004	11/23

Endpoints will be assessed over a period of up to 60 months after HAV implantation.

- The **primary analysis** of the study will be based conducted on the earlier of a) when the final patient enrolled reaches 12 months post-implant or b) all subjects enrolled in the initial 36 month accrual period have reached 12 months post-implant. The SAP will call this the 1-year analysis.
- The **final analysis** will occur at the end of the study, when all patients have completed or exited the study.

The database extraction for the **1-year analysis** will include all study data collected at the time of the database extraction. The by-visit tables and figures will display all time points present in the data, including visits after the Month 12 visit (where applicable). Event tables (such as concomitant medications, AEs), will include all events during the study. Listings will display all study data available, including data collected after the Month 12 visit.

The database for the final analysis will include all study data and by-visit tables will display all study timepoints.

4 Statistical Evaluation

All tables, figures and listings will be produced using SAS (v9.4 or a more recent version).

Unless otherwise stated, categorical data will be presented using counts and percentages, whilst continuous parameters will be summarized using standard summary statistics as appropriate (n, mean, standard deviation [SD], median, minimum, maximum, 25th percentile, and 75th percentile). Minima and maxima will be quoted to the number of decimal places as recorded in the case report form (CRF); means, SDs and medians will be quoted to one further decimal place.

The closest non-missing values prior to implantation on Day 1 will be used as baseline values.

Unless otherwise stated, all confidence intervals will be presented as 95% two-sided intervals. For categorical endpoints, if all values are either success or failure, the exact CI will be presented.

As no sample size assessment has been undertaken, all analysis results are considered to be exploratory.

Details on the specification, definition, calculation and analysis of the efficacy and safety endpoint variables are given in Section 2 and the following sections.

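### Non-serious local inflammation and anastomotic bleeding that start after Month 12 have no clear reporting route, so any study-long incidence of these two primary safety components is a lower bound

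*Protocol*

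**What the plan says.** Protocol section 8.5 sets two reporting periods. General adverse event reporting starts at implantation and "ends at the conclusion of the Month 12 or ET visit unless an unresolved AE is still being followed". After that the rule is "During the long term follow up period from post Month 12 through Month 60, only the following will be reported by the investigator": all SAEs and all Events of Special Interest. Footnote 7 of Appendix 1 repeats this for the Month 18 to Month 60 column.

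The primary safety endpoints in section 4.2.1 include "Significant local inflammation at the HAV implantation site" and, as one combined item, "Anastomotic bleeding or spontaneous rupture". The Events of Special Interest in section 8.4 include "HAV spontaneous rupture", as well as occlusion, infection, abandonment, aneurysm, pseudoaneurysm and excision. Neither local inflammation nor anastomotic bleeding is on that list.

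On the time horizon, section 4.2 says "Endpoints will be evaluated at multiple time points up to 60 months after HAV implantation". It then times the primary analysis at 12 months after implantation. SAP section 6 tabulates and lists HAV complications, naming both event types, and states no cut at Month 12.

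**The concern.** A primary safety component needs the same reporting rule over the whole period in which it is counted. Here, two components have full capture for 12 months and restricted capture for the next 48, while the others are reportable throughout. If the HAV-complication table counts events over all study time, few late cases of inflammation or anastomotic bleeding could reflect either their rarity or the reporting rule. The table would not show which.

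This matters more for inflammation. Protocol section 2.5.1 names an immune response that could damage the vessel as a possible risk, to be assessed by PRA, and section 7.3.1 measures PRA only at screening and Month 6. Linking late local inflammation to such a response is an inference, not a statement in the protocol. Even so, the plan has no scheduled immunological test after Month 6. With 15 patients recruited (SAP section 1.5), one unreported case moves an incidence by 1/15 = 6.7 percentage points.

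**Working it through.** The plan states no event rate or capture figure on this point, so there is nothing to reproduce. The check sets the sections side by side and then bounds the effect.

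**Step 1. Primary safety components (4.2.1) against the post-Month 12 list (8.4).**

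| Component | On the 8.4 list? | Reportable after Month 12 |
|---|---|---|
| Aneurysm or pseudoaneurysm | Yes, both | All |
| Spontaneous rupture | Yes | All |
| Anastomotic bleeding | No | If an SAE |
| HAV infection | Yes | All |
| HAV removal | Yes, as excision | All |
| Significant local inflammation | No | If an SAE |

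The remaining primary safety item, overall frequency and severity of adverse events, is not an event type and is openly cut back by the same rule.

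**Step 2. How much the SAE route catches.** Section 8.2 counts as serious any HAV event that leads to a surgical or endovascular intervention, along with hospitalization and the usual criteria. Section 8.5.5 requires SAE reports through Month 60. What remains is events managed without any of these.

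**Step 3. Whether another route exists.** Section 8.5.5 extends its reporting to adverse events of any kind that bear on participants' safety or on the running of the study. That conflicts with the word *only* in section 8.5 and depends on site judgment. Section 7.2 is narrower again and lists only SAEs associated with the HAV. The HAV site is examined at every long-term visit (7.5.4), so a late finding can be seen. But the data review meeting in SAP section 8 identifies complications from adverse event data. Examination results go elsewhere: the focused vascular exam to a listing (SAP 4.4.4) and the physical exam to a shift table from baseline to final visit (SAP 5.2).

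**Step 4. Extent of the restricted period.**
- 60 − 12 = 48 months; 48/60 = 80% of planned follow-up.
- 15 patients × 4 years = 60 patient-years at most, if nobody leaves early.

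**Step 5. Illustration of the undercount.** Let *f* be the share of events with onset after Month 12, and *q* the share of those that are non-serious and not otherwise reported. Then the share captured = 1 − *f* × *q*. Both inputs are assumptions.

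| *f* | *q* = 0 | 0.25 | 0.5 | 0.75 | 1 |
|---|---|---|---|---|---|
| 0.1 | 100% | 97.5% | 95% | 92.5% | 90% |
| 0.3 | 100% | 92.5% | 85% | 77.5% | 70% |
| 0.5 | 100% | 87.5% | 75% | 62.5% | 50% |
| 0.8 | 100% | 80% | 60% | 40% | 20% |

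The row *f* = 0.8 corresponds to a constant event rate with complete follow-up. Across the grid the undercount runs from 0% to 80%. If both event types were reportable to Month 60, capture under the rule would be 100% for any *f* and *q*.

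**The case against.** The strongest reply is that this is a deliberate and reasonable structure: full capture to the primary analysis, then targeted capture. Section 9.2 times the safety analyses at 12 months, and section 4.2.3 names the long-term endpoints without including either event. A late anastomotic bleed that needs neither intervention nor hospitalization is hard to picture. The study is exploratory, with no hypothesis test. Complications are listed with time to onset, so a careful reader could see when they occurred.

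Much of this stands. It limits the gap to non-serious late events, makes it more plausible for inflammation than for bleeding, and leaves Month 12 incidence intact. It does not settle what the study-long table means. Section 4.2 puts the endpoint horizon at 60 months, section 11 promises a report addendum with data to 60 months, and SAP section 6 sets no cut. Elsewhere the SAP does limit summaries to Month 12, for example duplex results in 4.4.1. Onset times of recorded events cannot reveal events that were never recorded.

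A reader might infer that the final report is bound to present all components as if equally ascertained, citing "Event tables (such as concomitant medications, AEs), will include all events during the study" in SAP section 3.4. That sentence describes the 1-year extraction, and nothing in the SAP says ascertainment is equal. A reader might also point to the predecessor PAD study (protocol section 2.4.3), where local swelling occurred in 15% of 20 patients, that is 3, and was not among the SAEs reported by two or more. Swelling is not significant local inflammation and no onset times are given, so it does not measure late events.

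**Conclusion.** The point holds in a limited form. One primary safety endpoint and half of another are missing from the list that governs reporting after Month 12. Their non-serious late occurrences have no clear route into the data used to identify HAV complications. A study-long incidence for these two components mixes full with restricted capture and should be read as a lower bound.

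The restricted rule covers 80% of planned follow-up, but that is not the size of the undercount. The 0% to 80% range rests on assumed values of *f* and *q*, and the documents supply neither.

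The stronger reading, that two whole primary endpoints will be undercounted because sites are told to withhold them, is not supported. Spontaneous rupture is listed, serious events are reported to Month 60, section 8.5.5 offers a further though conflicting route, and whether any event is missed depends on whether non-serious late events occur.

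**What to change.** In SAP section 6, present HAV-complication incidence for significant local inflammation and anastomotic bleeding through Month 12. Show later events separately, with a footnote that only serious events of these two types were systematically reported after Month 12. This costs one table split and a footnote, and it corrects the interpretation whether or not the protocol changes.

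Prospectively, add both terms to the post-Month 12 reporting list in protocol sections 8.4 and 8.5. At the same time, reconcile the three statements of scope: *only* SAEs and Events of Special Interest in 8.5, the wider safety clause in 8.5.5, and the HAV-associated SAEs in 7.2.

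The cost is a protocol amendment and slightly more event reporting. Events of Special Interest carry a 24-hour report and detailed notes within 48 hours under section 8.5.6. An amendment cannot recover late events that already went unreported, so the SAP split is needed in either case.

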# 8.5.1. Criteria for Determining Causal Relationship to the HAV and Criteria for Determining Causal Relationship to the Index Surgical Procedure

The criteria for determining the causal relationship of an AE with the HAV are presented in the table below. A separate assessment of causal relationship of an AE to the index surgical procedure is required as well using the same criteria and definitions presented in the table below. Please note that causal relationship to procedure only refers to the index surgical procedure in which the HAV was initially implanted.

Causal Relationship to the IP	Criteria for Determining Causal Relationship
Definitely Related	There is clear evidence to suggest a causal relationship, and other possible contributing factors can be ruled out. The clinical event, including an abnormal laboratory test result, occurs in a plausible time relationship to surgical placement of the HAV and cannot be explained by concurrent disease or other devices, drugs, or chemicals.
Possibly Related	There is some evidence to suggest a causal relationship (e.g., the event occurred within a reasonable time after the surgical placement of the HAV). However, the influence of other factors may have contributed to the event (e.g., the subject's clinical condition, other concomitant medications). Although an adverse event may rate only as "possible" soon after discovery, it can be flagged as requiring more information and later be upgraded to certain as appropriate.
Unlikely Related	A clinical event, including an abnormal laboratory test result, whose temporal relationship makes a causal relationship improbable (e.g., the event did not occur within a reasonable time after surgical placement of the HAV) and in which other drugs or chemicals or underlying disease provide plausible explanations (e.g., the subject's clinical condition, other concomitant treatments).
Not Related	A clinical event, including an abnormal laboratory test result, which occurs when the HAV was not implanted; or, another cause is obvious and in which there is sufficient information that the etiology of the event is not related to the HAV.

The sponsor will make the final determination of causality for the purposes of reporting to the regulatory authorities and to the Principal Investigators.

#### 8.5.2. Criteria for Defining the Severity of an Adverse Event

Severity of adverse events, including abnormal clinical laboratory values, will be assessed according to the criteria below and entered in the eCRF:

Grade	Severity Assessment Standard
1-Mild	Events require minimal or no treatment and do not interfere with the subject's daily activities.
2-Moderate	Events result in a low level of inconvenience or concern with the therapeutic measures. Moderate events may cause some interference with functioning.
3-Severe	Events interrupt a subject's usual daily activity and may require systemic drug therapy or other treatment. Severe events are usually incapacitating.
4-Life-threatening	Any adverse event that places the subject or participant, in the view of the investigator, at immediate risk of death from the reaction as it occurred, i.e., it does not include a reaction that, had it occurred in a more severe form, might have caused death.
5-Death	Death related to AE.

#### 8.5.3. Reporting of Action Taken to Resolve AE

- None
- Lab tests / further evaluation
- Treatment required (specify if hospitalized)
- Patient withdrawn from study
- Other (specify)

#### 8.5.4. Reporting the Outcome of the AE

- Recovered, with sequelae
- Recovered, without sequelae
- Ongoing
- Death

Confidential

Humacyte, Inc. Study No. CLN-PRO-V004

• Lost to follow-up

#### 8.5.5. Reporting Serious Adverse Events

The urgency for reporting SAEs is 4-fold: (1) to facilitate discussion (and implementation, if necessary) by the sponsor and the investigator of appropriate follow-up measures, (2) to facilitate investigator reporting of unanticipated problems involving risk to human subjects to the institutional review board (IRB), (3) to facilitate the sponsor's rapid dissemination of information regarding AEs to other investigators/sites in a multi-center study, and (4) to enable the sponsor to fulfill the reporting requirements to the appropriate regulatory authority.

Any SAE that occurs through Month 60, whether or not causally related to the IMP, must be reported by the investigator or designee to the Safety CRO within 24 hours of learning of its occurrence. This applies also to any AE that could affect the safety of the study participants or the conduct of the study.

Information about an SAE will be collected and recorded on the SAE Report Form. The investigator must assess the relationship to the investigational product and any relevant procedure.

The investigators must complete the SAE Report Form in English, and **send the completed**, signed form by fax or email (see below) IMMEDIATELY (at latest within 24 hours) after becoming aware of the SAE.

Copies of relevant medical records (e.g., admission and/or discharge summary, laboratory reports and autopsy report), may also be submitted with the SAE form to clarify the circumstances surrounding the SAE(s). The entire medical records should **NOT** be sent with the SAE form.

Atlantic Research Group, Inc. Drug Safety Department [contact] Email: [contact] [contact]

The investigator will be requested to supply as much detailed information as possible regarding the SAE that is available at the time of the initial contact. The investigator should also complete missing or requested information and submit follow-up reports until the SAE has resolved or, in the case of permanent impairment, until the SAE has stabilized.

It is the responsibility of each Principal Investigator to promptly notify his/her IRB of all SAEs that are received by the Sponsor or designee and that occur at his/her institution in accordance with institutional practices.

The Safety CRO will inform the sponsor about all SAEs within 1 business day after receipt of the respective report from the investigator.

